4. STUDY DESIGN/TIMELINE/ AND RESEARCH SITES

4.1 Study Design:

To address these questions we will identify opioid addicted prisoners who appear to meet study admission criteria and express interest in XR-NTX treatment, explain the study to them in detail, encourage them to ask questions, and obtain consent from those who remain interested. We will then complete baseline assessments to confirm eligibility (criteria described later) and the first 200 that meet enrollment criteria will be stratified according to male/female and sentenced/not sentenced (e.g. meet/not meet with probation/parole officer), and randomized 1:1 to receive XR-NTX before reentry with the offer of having three additional doses of XR-NTX at NET Steps after reentry, or be given an appointment to be seen at NET Steps same day or up to 7 calendar days after release to receive their first dose of XR-NTX after reentry with the opportunity for 3 additional doses at NET Steps. Follow-ups for participants who have difficulty going to the NETSteps site can have their follow-up injections and assessments done at the [name]. All participants will be assigned a Patient Benefits Manager to help reinstate benefits that were lost during incarceration and all will receive the usual counseling and other services available to NET Steps patients (described later in more detail). A urine drug toxicology screen , adverse events, and an alcohol breathalyzer test will be done weekly and brief assessments will be done at months 1, 2, 4 and 5 with more detailed assessments at months 3 and 6. Criminal justice information on arrests and re-incarcerations will supplement the assessments.

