13 STATISTICAL HYPOTHESES AND PLAN

13.1 Primary Aims

Before performing analyses, we will apply the following data screening and cleaning procedures: 1) screen for data-entry errors; 2) check for outliers; 3) assess the extent and pattern of missing data, and 4) check that appropriate assumptions of normality are met, as necessary. In all analyses, we will examine whether the assumptions underlying the application of statistical methods have been met, principally through use of standardized residuals, influence diagnostics, and graphical displays. We will check to confirm that the groups do not differ on baseline relevant background variables using analyses of variance (ANOVA) for continuous variables and log-linear models for binary or ordinal responses. The randomization process should minimize the need for inclusion of covariates to reduce bias in treatment comparisons. However, we will consider relevant covariates for inclusion in analyses to improve precision of estimation of treatment effects (Hauck et al. 1998). The statistical procedures that will be used to examine each outcome are listed below.

13.2 Primary Aim 1—Proportion Without Relapse by Month 3:

At each monthly assessment we will determine whether a subject has relapsed based on self-report, physical examination, response to a naloxone challenge, or information from program staff of significant others. Using these data, we will create a binary outcome reflecting whether or not the participant relapsed during the 3 months post-release. We will compare the proportion of participants who relapsed in the two groups using a logistic regression analysis. The analysis will include group as a predictor variable along with all relevant covariates (including the stratification variables). Relapsed will be defined by self-report of 10 or more days in the past 30 days or by two or more opiate positive urine samples in the last 30 days. Positive urine samples will be computed as 5 days of opioid use for each sample. The analysis will be performed using SAS's PROC LOGISTIC.

13.3 Power Analyses for Primary Aim:

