There are relatively few data to estimate power for this study since so little work has been done in this area. We know that most relapses from various substance dependencies occur in the first 3-6 months ([name] & Cacciola, 1994). For opioid addiction it typically occurs in the first days or weeks (Binswanger et al, 2007) and for opioid addicted prisoners, often on the way home from jail, according to reports from the two Recovery Specialists and

more than half of the focus group participants. We also know that XR-NTX will prevent relapse for a month and that more than twice as many prisoners that did not receive it before reentry relapsed by the second month after reentry as compared with those that received it before reentry (Lee et al, 2013). Regarding the issue of how long patients will continue on XR-NTX, 79% of the XR-NTX patients in the O'Brien et al study received their first 3 injections and 73% received their first 4. In the Krupitsky et al study (2011) 78% received their first 3 injections and 70% received their first 4 (data provided by [name], Alkermes, 2014).

The Lee et al study most closely resembles the one proposed here, however our study has a stronger control group than Lee et al because patients in our control group will be offered XR-NTX at NET Steps after reentry and all participants will have a Patient Benefits Manager to help reinstate benefits that were lost while incarcerated. Putting these data together, we estimate a 23-33% group difference in relapse rates by month 3. Power estimates calculated using this estimate and following the recommendations of Cohen with a 2-sided alpha of .05 and a baseline sample size of 100 per group result in 80% power to detect a difference in relapse rates of approximately 20% (OR = 2.4) between the two groups assuming a relapse rate of 50% in the control condition and 10% and 20% attrition by the 3- and 6-month follow-ups. These outcomes are clinically meaningful based on the severe consequences from untreated opioid addiction, the evidence that continuing in treatment reduces them, and confirmation of their importance by conversations with ex-prisoners and the Recovery Specialists, and focus group participants.

13.4 Secondary Aims:

- 1) Quality of life;
- 2) Weeks in treatment through month six;
- 3) Time to relapse;
- 4) Rearrests;
- 5) Psychiatric symptoms;
- 6) Opioid use;
- 7) Alcohol and other drug use;
- 8) HIV risk;
- 9) Reincarceration;
- 10) Deaths.

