We will use linear mixed effects models (Littell, Milliken, Stroup, & Wolfinger, 1996) to examine group differences on continuous longitudinal outcomes (i.e., 1) quality of life scores, 5) Psychiatric symptoms, 8) HIV risk scores,) and non-linear mixed effects models (Diggle, Heagerty, Liang, and Zeger, 2002) to compare the groups on binary longitudinal outcomes (i.e., 6) opioid, 7) alcohol, and other drug use). Mixed effects models have advantages over conventional repeated measures methods as they allow for missing observations, provide greater flexibility in modeling the variance-covariance matrix, and permit the estimation of both group and random subject-specific effects. Models will be calculated using SAS's PROC GLIMMIX and MIXED, respectively. We will use a Poisson regression model to compare the groups on 2) weeks in treatment through month 6. We will use a Cox proportional hazards regression model to determine whether the time to relapse (3) differs across the two groups. The analysis will account for the fact that the data will likely be right-censored as some participants may experience a relapse during the period of observation. The analysis will include relevant covariates and will be performed using SAS's PHREG. The models will include a terms for group, time, and their interaction as well as any necessary covariates. Finally, we will use logistic regression to compare the two groups on binary cross sectional outcomes (i.e., 4) rearrest, 10) death, and 9) reincarceration). The models will be similar to that described for the primary outcome.

13.5 Missing values:

Missing data will not be an issue for several of the outcomes (i.e., days in treatment, re-arrest, re-incarceration). The most important source of missing data is likely to be dropout. As recommended by Lavori (1992), we will analyze the data under an intent-to-treat principle, in which all participants initially randomized will be included. Logistic regression models predicting dropout, based on patient characteristics and prior measures, will be used to determine whether the dropout process is ignorable (i.e. whether missed visits are well explained by observable data). Although these models provide a formal framework for assessing sensitivity to missing data, much of their implementation proceeds in an exploratory manner.

13.6 Maintenance of Data on Retention Efforts:

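### Time to relapse is assigned a Cox proportional hazards model although the plan's own premises make a constant hazard ratio implausible, and no horizon, fallback or common time origin is fixed

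*Combined protocol and SAP*

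**What the plan says.** Section 13.4 assigns outcome 3 to a Cox model fitted in PHREG with relevant covariates: "We will use a Cox proportional hazards regression model to determine whether the time to relapse (3) differs across the two groups". The next sentence but two reads: "The models will include a terms for group, time, and their interaction as well as any necessary covariates". It does not say which of the section's models it covers. No horizon is given for the Cox analysis. Follow-up per participant is six months (Protocol Summary) and the primary endpoint is at month 3.

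Section 13.1 makes a general commitment: "In all analyses, we will examine whether the assumptions underlying the application of statistical methods have been met", using residuals, influence diagnostics and graphs. It names no check of proportional hazards and no substitute analysis.

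Three other places describe how the hazards should behave:

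- Section 13.3 says "We also know that XR-NTX will prevent relapse for a month". It also says that opioid relapse usually happens within days or weeks, and for prisoners often on the journey home.
- Section 4.1 doses the pre-release arm (Group A in Section 5.5) before reentry. It gives the other arm (Group B) an appointment "to receive their first dose of XR-NTX after reentry with the opportunity for 3 additional doses at NET Steps".
- Group B's first-dose window is up to 7 days after release in Sections 4.1 and 5.5, but up to 30 days in Section 5.1.

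Section 8.1, item 10, starts the time-to-relapse clock when physiologic dependence is absent. Section 13.2 counts the primary outcome over the 3 months after release.

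**The concern.** The design contrasts cover at release with no cover at release, followed by an offer of the same treatment to both arms. On the plan's premises the arms should differ most in the first weeks and less afterwards. A Cox model with a single group coefficient averages such a pattern over the observed event times, so the result depends on how long people are followed and how they are censored. Three months and six months would give different hazard ratios from the same trial, and the plan does not say which is meant.

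Two things are at stake. The reported ratio would have no fixed meaning. And if the effect is mainly early, the test may be less sensitive than an available alternative on the same data. If the assumption check fails, the replacement would be chosen after the curves are seen, in a trial that Section 16.2 describes as not double blinded.

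**Working it through.** **Step 1. The plan's only power figure.** It belongs to the primary binary outcome. Inputs from Section 13.3: "with a 2-sided alpha of .05 and a baseline sample size of 100 per group", "assuming a relapse rate of 50% in the control condition and 10% and 20% attrition by the 3- and 6-month follow-ups", giving "result in 80% power to detect a difference in relapse rates of approximately 20% (OR = 2.4) between the two groups". With 10% attrition, n = 90 per group.

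Power = Φ{[|p1 − p2|√n − 1.96√(2p̄q̄)] / √(p1q1 + p2q2)}

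For 50% vs 30%: (0.20 × 9.487 − 1.96 × 0.6928) / 0.6782 = 0.795, so power is 0.787. For OR 2.4 (29.4% relapse) it is 0.811. The stated 80% reproduces. No power, event count or hazard ratio is stated for time to relapse.

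**Step 2. What a proportional effect of that size would be.** HR = ln 0.70 / ln 0.50 = 0.515. Events = 90 × 0.5 + 90 × 0.3 = 72. Schoenfeld power = Φ(√(72/4) × 0.664 − 1.96) = 0.805.

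**Step 3. An early-effect pattern.** The documents give no hazards, so these are assumptions: month-1 relapse 30% in B and 8% in A, then 15% per month in both.

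- Month-3 relapse: B = 1 − 0.70 × 0.85² = 49%; A = 1 − 0.92 × 0.85² = 34%.
- Hazard ratio in month 1: ln 0.92 / ln 0.70 = 0.23. Afterwards: 1.
- Simulated Cox HR: 0.22 over 4 weeks, 0.54 over 12, 0.66 over 24.

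**Step 4. Power on the same simulated data.** Set-up: 100 per arm, piecewise-exponential relapse times, exponential dropout of 20% by month 6 (which implies 1 − √0.8 = 10.6% by month 3, close to the plan's 10%), two-sided 0.05, no covariates, at least 1,500 replicates for patterns 1 and 3. One month is taken as 4 weeks in patterns given as monthly rates.

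| Assumed pattern | Month-3 relapse, B vs A | 3 months: HR; Cox / RMST power | 6 months: HR; Cox / RMST power |
|---|---|---|---|
| 1. Step 3 pattern | 49% vs 34% | 0.54; 77% / 94% | 0.66; about 60% / 79% |
| 2. Month 1 as in 1, then 15% (B) vs 13% (A) monthly | 49% vs 30% | HR not computed; 88% / 96% | HR not computed; about 81% / 90% |
| 3. No relapse in A in month 1, equal hazards after | 50% vs 30% | 0.44; 94% / 99.9% | 0.60; 80% / 95% |
| 4. Proportional hazards | 50% vs 30% | 0.51; 82–84% / 75% | 0.51; 94–95% / 93% |

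Over 4 weeks alone, Cox is slightly better than RMST in pattern 1.

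**Step 5. Does the Cox test lose power in absolute terms?** Compare pattern 3 with two proportional alternatives.

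- Same month-3 rates (pattern 4): Cox power is higher at 3 months (94% vs 82%) and lower at 6 months (80% vs 95%).
- Same 6-month rates (71% vs 59%): Cox power at 6 months is higher (80% vs 42%).

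The direction depends on the horizon and the comparator. Only the comparison with RMST on the same data points one way in the front-loaded patterns, at 3 and 6 months.

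**Step 6. The clock.** Section 8.1, item 8, uses the naloxone challenge to establish absence of dependence. Section 5.5 schedules that challenge before release for Group A and after release for Group B. If the challenge dated the start, the arms would start at different points relative to release, and Group B's first uncovered days would fall before time zero. The text does not say that it does, but it does not rule it out.

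**The case against.** **The plan may already allow a time-varying effect.** A group-by-time term is the usual way to relax proportional hazards, and the sentence that promises one comes soon after the Cox sentences. A reader might infer that the plan commits to one constant ratio; the text does not establish that. It does not settle the opposite either. A main effect of time has no role in a Cox model, where the baseline hazard absorbs it, so the wording suits the longitudinal mixed models better. If it does apply, neither the form of time nor the coefficient that answers the question is given. The ambiguity stands on either reading.

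**The ratio need not move to 1.** A reader might infer that the hazard ratio must approach 1, or exceed it, after the first month. The documents do not support that. Being offered the drug is not receiving it: Group B must attend, test opioid-negative and pass the challenge first (Section 5.5). Non-attenders who have not relapsed stay uncovered, so a difference can persist. Conversely, Group B may be dosed on the day of release, which narrows the early contrast. Either way there is no reason to expect a constant ratio, but its path is not known.

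**Weak assumed effects exaggerate the problem.** Pattern 1 has a 16-point difference at month 3, below the plan's design effect of about 20 points and its expected 23–33. Near the design effect (patterns 2 and 3) Cox keeps at least 80% power at 6 months. RMST still leads there, but all these patterns assume an early effect. Under proportional hazards the order reverses. This objection stands as to size.

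**Assumptions will be checked.** True, but no action is named if the check fails.

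**Conclusion.** The concern holds for a secondary outcome and should be addressed before analysis. A constant hazard ratio is implausible on the plan's own account of when the drug acts and when relapse occurs. As written, the reported ratio would depend on an unstated horizon: 0.54 to 0.66 between 12 and 24 weeks in pattern 1, and 0.44 to 0.60 between 3 and 6 months in pattern 3.

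Against RMST on the same data, Cox gives up about 19 points of 24-week power in pattern 1 (60% vs 79%) and about 9 in pattern 2 (81% vs 90%). Under proportional hazards Cox gains about 1 point at 24 weeks (94% vs 93%) and about 9 at 12 weeks (84% vs 75%). All of these rest on assumed hazards and unadjusted tests.

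A reader might infer that the trial loses planned power, or that a real benefit will be missed. The documents do not support that: no power is stated for this outcome, Step 5 shows that the direction depends on the comparator, and the month-3 logistic regression tests the main hypothesis regardless of how this is resolved.

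**What to change.** Amend Section 13.4 before analysis:

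1. Make the comparison for outcome 3 the difference in restricted mean time to relapse through month 6, and also through month 3, adjusted for the stratification factors and shown with Kaplan-Meier curves.
2. Report the Cox model alongside it, with separate hazard ratios for the first 30 days and for the rest of follow-up. State whether the group-by-time sentence applies to this model.
3. Use one time origin for both arms, reconciling Section 8.1, item 10, with the post-release period of Section 13.2.
4. Reconcile the 7-day window for Group B's first dose (Sections 4.1 and 5.5) with the 30-day window (Section 5.1), because it determines how long the arms differ in cover.

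The cost is a few sentences and a few lines of code. The drawbacks are that there is no single hazard ratio to quote, that power falls by a small to modest amount if hazards are in fact proportional, and that RMST showed slightly liberal type I error in simulation (5.2% at 12 weeks and 5.6% at 24, against 5.2% and 5.0% for Cox; 4,000 replicates).

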15. PROTECTION OF HUMAN SUBJECTS AND CONFIDENTIALITY

Informed consent to participate will be voluntary, participants can drop out of the study at any time, and persons sentenced to naltrexone will be excluded. Informed consent will include information about the pharmacology of XR-NTX and its possible side effects (described below and in “package insert” found in Physician’s Desk Reference). There may be unanticipated situations where the investigator reserves the right to terminate a subject’s participation. Such situations would likely entail the development of a serious adverse event or new findings that impact the conduct of the study. Participants will be told that if suicidal or homicidal ideation develops that is judged to pose a significant risk to themselves or others, staff will be obligated to take emergency action that may involve communicating with a third party or involuntary commitment to a psychiatric facility. Urine and alcohol breath test results that are part of the study will not be shared with treatment staff, prison administrators, or probation or parole officers, a Confidentiality Certificate will be obtained once the study has been approved to protect data from forced disclosure, and patients will be informed of this protection. However they will be told that this Certificate will not prevent research or treatment staff

from disclosing evidence of child abuse or threatened violence to self or others.

In the event that a participant fails the naloxone challenge by testing positive for opioid use, the research clinical staff (study physician and/or nurses) will treat and observe him until the withdrawal symptoms caused by the naloxone challenge are resolved. This will be done in a private room in the medical suite. Information about the participant's drug use symptoms will not be reported to the PPS administrators or staff.

The informed consent will state that contact information may be shared with research staff to help locate participants for follow-up. At baseline, a medical examination will be done to rule out individuals that are suicidal, homicidal, psychotic, or have medical problems that may make it difficult or impossible to participate, or are unable to provide informed consent. Approvals from - IRBs serving the University of Pennsylvania and the PPS will be necessary. XR-NTX was approved for treatment of alcohol dependence in 2005 and for opioid dependence in 2010 and has been used with few serious adverse events among thousands of patients. Potential risks are summarized below.

In the

15.1 Study-Related Medical Problems: All patients will be provided with a study identification card stating that they are in a study of XR-NTX. Those that have a medical emergency will be told to consult with a study physician, their primary care provider, or go to the nearest emergency room and tell them if they have received XR-NTX in the last 30 days. Patients will be told to tell the doctor or other medical staff that they are in a research study being conducted at the University of Pennsylvania and ask them to call the telephone numbers that are listed on the study identification form for further instructions or information. In the event that a patient is hurt or injured as a result of participation, he/she is to contact the investigator listed on the consent form and study identification card. In the event of physical injury resulting from research procedures, medical treatment will be provided without cost to the patient but the University of Pennsylvania will not provide financial compensation. The patient's insurance will be responsible for the cost of medical care if the patient has an illness or injury that is not directly related to participation in the study.

The DSMB will review this study as indicated above and make recommendations to continue, amend, or terminate it based on safety data (e.g., terminate a trial because of high incidence of a particular SAE that is related to the study). This study is not double blinded, so the DSMB will be able to compare group outcomes and determine whether it should have an early termination. The DSMB will review study performance (e.g., protocol violations, improper entry criteria, slow accrual, low participation, failure of randomization, inadequate treatment adherence, inadequate follow-up rate, severely compromised validity), and independently make recommendations for improvement or termination if the trial is judged unable to prove anything meaningful.

16.3 Annual Reviews by the Penn and City IRBs: In addition to reviews by the Center's DSMB, PCORI requires annual reports of study progress including AEs and SAEs, and the Penn and City IRBs require annual reviews that include AEs and SAEs and can stop the study if they detect problems that justify it.

17. QUALITY ASSURANCE

17.1 Study Monitoring and Quality Assurance: A Quality Assurance Monitor is budgeted for this study (see budget justification). The monitor will review data and submit audit reports monthly using forms similar to those used in CTN studies such as the buprenorphine-naloxone study of opioid-addicted youth. The P.I., Project Director, and Co-Investigators will review reports and follow up to correct identified problems.

18. ETHICAL CONSIDERATIONS:

This study will be conducted according to US and international standards of Good Clinical Practice (FDA Title 21 part 312; International Conference on Harmonization guidelines) and all applicable governmental regulations and institutional policies and procedures. The protocol and any amendments will be submitted to the Penn and City IRBs for approval before procedures are changed unless they require immediate action to protect participants' safety.

All subjects will be given a copy of the consent describing the study with sufficient information to make an informed decision about participation. Information obtained in connection with the study that can be used to identify participants will be kept confidential, and any decision about study participation will be independent of decisions made by the PPS or other members of the criminal justice system on the legal status of participants. An informed consent will be written and submitted along with the protocol for review by the Penn and City IRBs if this study is to be funded. No study procedures will be commenced unless the participant has reviewed and been given the opportunity to ask questions about the purpose and procedures in the study, understands the risks and benefits, and signs the informed consent. The research team will apply for a Federal Confidentiality Certificate and no patients will be enrolled until it has been approved.

19. PUBLICATION PLAN:

The main findings will be submitted for presentation and dissemination at criminal justice, state, city and addiction treatment meetings as described in the dissemination plan, and to one or more refereed journals after data lock. Additional papers will be submitted later based on a publication plan developed during the study.

